5.6.3. Prohibited Medications

Medications or vaccinations specifically prohibited in the exclusion criteria (see [Section 4.2](#)) are not allowed during the ongoing study. If there is a clinical indication for one of these medications or vaccinations specifically prohibited during the study, discontinuation from study drug may be required. The investigator should discuss any questions regarding this with the medical monitor. The final decision on any supportive therapy or vaccination rests with the investigator and/or the subject's primary physician. However, the decision to continue the subject on study drug or vaccination schedule requires the agreement of the investigator, the sponsor, and the subject.

Subjects are prohibited from receiving the following therapies during the screening and treatment periods of this study:

- Any anticancer medications, including chemotherapy or biologic therapy other than the study drug.
- Any immunological-based treatment for any reason from screening through safety follow-up visit.

Note: Completed adjuvant therapy (e.g., vaccines) with medical monitor approval.

Note: Inhaled or topical steroids and systemic steroids at doses ≤ 10 mg/day prednisone or equivalents are allowed.

Note: Immune suppressants are allowed for treatment of immune toxicities as described in [Section 5.4.7](#) and Brahmer et al. ([Brahmer 2018](#)).

Note: Allergy shots may be permitted after consultation with the medical monitor.

- Investigational agents other than the study drug from screening through the follow-up visits.
- Concomitant radiation therapy.

Note: Radiation therapy to a symptomatic solitary lesion or to the brain may be considered on an exceptional case-by-case basis after consultation with the medical monitor. The subject must have clear measurable disease outside the radiated field. Administration of palliative radiation therapy will be considered clinical progression for the purposes of determining PFS.

- Live vaccines within 30 days before the first dose of study drug *and* while participating in the study. Examples of live vaccines include, but are not limited to, the following: measles, mumps, rubella, chicken pox, yellow fever, rabies, *Bacillus Calmette–Guérin*, and typhoid (oral) vaccine. Seasonal influenza vaccines for injection are generally killed virus vaccines and are allowed. However, intranasal influenza vaccines (e.g., *FluMist*[®]) are live attenuated vaccines and are not allowed.

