n The initial tumor imaging will be performed within 30 days before the first dose of study drug. Scans performed as part of routine clinical management are acceptable for use as the screening scan if they are of diagnostic quality and performed within 30 days before the first dose of study drug. The same imaging technique should be used for a subject throughout the study. Local reading (investigator assessment with site radiology reading) will be used to determine eligibility and for subject management.

o On-study imaging will be performed at Week 8 and then every 8 weeks (56 days \pm 7 days) for the first 6 months and then every 12 weeks (84 days \pm 7 days) thereafter. After completing 12 months of treatment, subjects will have imaging performed per standard of care and PI discretion. Imaging should follow calendar days and should NOT be adjusted for delays in cycle starts. If imaging shows disease progression, then another imaging assessment should be performed 4 to 6 weeks later to confirm progression per mRECIST.

p For subjects who discontinue for reasons other than disease progression, radiologic evaluation should be repeated at the time of treatment discontinuation (i.e., date of discontinuation \pm 4-week window). If scan was obtained within 4 weeks prior to the date of discontinuation, then a scan at treatment discontinuation (EOT) is not mandatory.

Table 8: Schedule of Local Laboratory Assessments

Visit Day (Range)	Protocol Section	Screening ^a	Treatment	Post-Treatment
			Day 1 of All Cycles	EOT
		Day - 30 to - 1	D1^{b,c}	
Evaluation/Window			Predose	
Comprehensive Metabolic Panel (CMP) ^d – serum	7.5.5	X	X	X
Complete Blood Count (CBC) with differential ^e	7.5.5	X	X	X
Coagulation panel ^f	7.5.5	X		X
Urinalysis ^g	7.5.5	X		X
Endocrine function tests ^h	7.5.5	X	X	X
Hepatitis B and C ⁱ	7.5.5.2	X		
Serum pregnancy test ^j (childbearing females only)	7.5.5.1	X ^j		X
Urine pregnancy test ^k (childbearing females only)	7.5.5.1		X ^l	

Abbreviations; CBC = complete blood count; CMP = comprehensive metabolic panel; D = day; EOT = end-of-treatment.

a Lab tests must be performed during screening period (within 30 day window).

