9.5.4. Efficacy Analyses

The response will be assessed by CT/MRI image during screening and every 8 weeks (\pm 7 days) post-dosing for 6 months and then every 12 weeks (\pm 7 days) thereafter (or per standard of care). The efficacy study endpoints include ORR, DCR, DoR, PFS, and OS. Tumor response will be determined according to RECIST v1.1. Time-to-event data (DoR, PFS, and OS) will be analyzed using the Kaplan-Meier method. All the efficacy data will be summarized by phase, dose group, and cohort.

- ORR includes RECIST v1.1 complete and partial response (CR or PR). ORR with 95% exact CI will be summarized by phase, dose group, and cohort.
- DCR includes RECIST v1.1 complete, partial response, and stable disease (CR, PR or stable disease). DCR with 95% exact CI will be summarized by phase, dose group, and cohort.
- DoR is defined as the duration from the first documented ORR to the first documented progressive disease or death due to any cause, whichever occurs first. For subjects who are alive and progression-free at the time of discontinuation from study, data cutoff for analysis, or use of other anti-cancer drug, DoR will be censored at the last tumor assessment date.

The DoR will only be analyzed for the subgroup of subjects with an objective response.

DoR = (progressive disease, death, or censored date) – (date of first response + 1)

- PFS is defined as from starting study treatment to the first documented progressive disease or death due to any cause, whichever occurs first. For subjects who are alive and progression-free at the time of discontinuation from study, data cutoff for analysis, or use of other anti-cancer drug, DOR will be censored at the last tumor assessment date.

PFS = (progressive disease, death, or censored date) – (date of first dose of study drug + 1)

- OS is defined as from starting study treatment to death due to any cause. For subjects who are alive at the time of discontinuation from study or data cutoff for analysis, OS will be censored at the date of last known alive (LKA).

OS = (Death or LKA date) – (date of first dose of study drug + 1)

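### The PFS, DoR and OS formulas come out one day short of elapsed time, and PFS censoring carries the wrong label and can fall before the first dose

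*Combined protocol and SAP*

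**What the plan says.** Section 9.5.4 (Efficacy Analyses) describes the time-to-event endpoints in words and then gives a formula for each. In words, PFS and OS run from the start of study treatment and DoR runs from the first documented response; no day is deducted. The formulas are:

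- "PFS = (progressive disease, death, or censored date) – (date of first dose of study drug + 1"
- "DoR = (progressive disease, death, or censored date) – (date of first response + 1"
- "OS = (Death or LKA date) – (date of first dose of study drug + 1"

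In each, the closing bracket follows the 1, so the added day belongs to the start date.

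For subjects "alive and progression-free at the time of discontinuation from study, data cutoff for analysis, or use of other anti-cancer drug", the DoR bullet says "DoR will be censored at the last tumor assessment date". The PFS bullet repeats the sentence and still names DOR as the quantity censored. Section 9.5.4 includes the screening scan in its description of response assessment, and footnote n to Table 7 states: "The initial tumor imaging will be performed within 30 days before the first dose of study drug". Under Section 9.1 the full analysis set requires one full dose and no post-baseline scan. Section 9 leaves further analysis detail to a SAP; the supplied text contains no rule for a subject without a post-baseline assessment.

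**The concern.** There are three separate faults.

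1. **Bracket.** Adding a day to the start date and then subtracting it removes a day. The formulas contradict the verbal definitions under either usual day count.
2. **Label.** Read literally, the PFS bullet gives a second DoR censoring rule and none for PFS.
3. **No floor at first dose.** If the last tumor assessment is the screening scan, the censoring date precedes the time origin.

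Programmed as printed, the text yields negative times, which are not valid input to the Kaplan-Meier analysis that Section 9.5.4 specifies. Someone would then have to devise a rule after seeing the data.

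**Working it through.** The plan states no figure that depends on these formulas, so there is nothing to reproduce. The check is date arithmetic.

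**Formulas.** Let d = end date − start date.
- As written: end − (start + 1) = d − 1
- Elapsed days: d
- Inclusive count: d + 1

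| Case | d | As written | Elapsed | Inclusive |
|---|---|---|---|---|
| OS: death or last known alive on first-dose day | 0 | −1 | 0 | 1 |
| DoR: censored at a confirmation scan 28 days after response | 28 | 27 | 28 | 29 |
| PFS: progression at 8 weeks | 56 | 55 | 56 | 57 |
| PFS: only scan 1 day before dose | −1 | −2 | −1 | 0 |
| PFS: only scan 28 days before dose | −28 | −29 | −28 | −27 |
| PFS: only scan 30 days before dose | −30 | −31 | −30 | −29 |

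Moving from the printed formula to the inclusive one adds exactly 2 days to every time, or 2 / 30.4375 ≈ 0.07 month.

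**Can the baseline scan be the last one with no scan missed?** There are two routes. Let s be the number of days from the baseline scan to first dose, 1 to 30 (Table 7 footnote n; Section 7.6.1.2).

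- *End-of-treatment scan waived.* Section 7.6.1.4 and Table 7 footnote p make that scan non-mandatory if one was obtained within 4 weeks before discontinuation. A subject who stops t ≥ 0 days after first dose qualifies on the baseline scan when s + t ≤ 28, so s is 1 to 28. If the subject then leaves the study or starts another anticancer drug before the next scheduled scan, PFS as written is −s − 1, that is −2 to −29. With the bracket corrected it is −s + 1, that is 0 to −27.
- *Data cutoff before the first on-study scan.* That scan is due at 8 weeks, 56 ± 7 days (Section 7.6.1.3). A subject on treatment at a cutoff up to day offset 62 may have only the baseline scan. With s from 1 to 30, PFS as written is −2 to −31, and 0 to −29 with the bracket corrected.

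The bracket correction is therefore not enough. With the inclusive formula and a floor at first dose, these subjects have censored PFS = 1.

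**DoR.** Section 9.5.4 says "ORR includes RECIST v1.1 complete and partial response (CR or PR" and closes the bracket without mentioning confirmation, whereas Section 7.6.1.3 says response should be confirmed at least 4 weeks later. If unconfirmed responses count, a responder whose last scan is the response scan has d = 0 and a DoR of −1 as written, against 0 or 1. If confirmation is required, this case does not arise.

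**Palliative radiation.** Section 5.6.3 states: "Administration of palliative radiation therapy will be considered clinical progression for the purposes of determining PFS". A floor rule must not override this. A living subject irradiated 35 days after first dose, with no post-baseline scan, should be a PFS event at 35 + 1 = 36, not censored at 1.

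**The case against.** The strongest reply is that the matter is editorial. The verbal definitions are clear, the mislabelled sentence stands in the PFS bullet just above the PFS formula, the shift is constant and preserves order, no formal test is planned (Section 9.3), and the stage rules use response counts (Sections 9.2.2.1 and 9.2.2.2). All of that is right about size. It does not make the printed formulas correct, and a later SAP could put them right only by contradicting the protocol.

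On the floor, Section 9 defers detail to a SAP that was not supplied, so a rule may exist there. That stands, and the point is limited to the supplied text.

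The cutoff route can also be questioned. Section 3.5 allows the study to be declared ended, with a database lock, when few subjects have remained on drug for at least 6 months, and Section 9.4 plans no formal interim analysis. At a final analysis on those terms, nobody should still be awaiting a week-8 scan. But Section 9.5.4 itself names a data cutoff as a censoring occasion, Section 9.4 foresees regular review of efficacy data, and Section 5.4.8 reports results at a mid-study cutoff. The route is open for such looks. The waiver route is narrow, and the documents do not show how many subjects would take it.

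Finally, the documents do not say which day count is intended, and elapsed days would also fit the verbal definitions. The printed formulas match neither. Nor does the PFS definition in Section 9.5.4 mention palliative radiation; that gap is a separate issue, which the floor rule should not worsen.

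**Conclusion.** The concern holds on all three parts and is minor. The bracket and label faults are plain on the face of Section 9.5.4 and need no assumption. All three endpoints are 1 day below elapsed time and 2 days below the inclusive count, without any change in the order of event times. The floor fault assumes that no unsupplied SAP text sets the rule, and that a subject reaches a censoring occasion with only a baseline scan. In that case PFS is −2 to −29 days by the waiver route or −2 to −31 by the cutoff route. The negative DoR value depends on unconfirmed responses being counted. No decision rule or test is affected; the practical harm is impossible times entering descriptive Kaplan-Meier summaries of secondary endpoints.

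**What to change.** Amend Section 9.5.4 as follows.

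- PFS = (progression, death or censoring date) − (first-dose date) + 1
- DoR = (progression, death or censoring date) − (first-response date) + 1
- OS = (death or last-known-alive date) − (first-dose date) + 1
- In the censoring sentence of the PFS bullet, replace DOR with PFS.
- Add a floor: a subject due to be censored for PFS under the existing conditions, with no post-baseline tumor assessment by that time, is censored at the date of first dose (Day 1). State that this applies only where there has been no clinical progression under Section 5.6.3, so that palliative radiation remains a PFS event.

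The inclusive form follows from the + 1 already in the formulas. If the sponsor prefers elapsed days, drop the + 1 from all three; the floor is still needed.

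The cost is one paragraph of wording, with no extra data and no burden on subjects. It should be done before database lock and carried into the SAP.

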9.5.5. Pharmacodynamic and Biomarkers Analysis

The PD and biomarkers are explorative for this study. These data will be listed only.

Descriptive statistics will be the primary methods for the exploratory analyses. Among the variables to be included in the exploratory analyses are:

- Correlation analysis between PD biomarkers and the disease response to treatment with NC318.

The immunogenic potential of NC318 will be assessed by summarizing the number and percentage of subjects who develop detectable ADAs. The impact of ADAs on PK will be assessed if data allow. Samples will be collected for evaluating neutralizing capacity of ADAs in the future.

9.6. Analyses for Data Monitoring Committee

No formal analysis will be performed for Data Monitoring Committee purposes.

10. STUDY AND DATA MANAGEMENT

10.1. Training of Study Site Personnel

Before the first subject is entered into the study, a NextCure representative will review and discuss the requirements of the Clinical Study Protocol and related documents with the investigational staff and train them in any study-specific procedures and system(s) utilized.

The Principal Investigator (PI) will ensure that appropriate training relevant to the study is given to all of these staff, and that any new information relevant to the performance of this study is forwarded to the staff involved.

The PI will maintain a record of all individuals involved in the study (medical, nursing and other staff).

10.2. Monitoring of the Study

During the study, a NextCure representative will have regular contacts with the study site, including visits to:

- Provide information and support to the investigator(s).
- Confirm that facilities remain acceptable.
- Confirm that the investigational team is adhering to the protocol, that data are being accurately and timely recorded in the eCRFs, that biological samples are handled in accordance with the NC318-01 Laboratory Manual and that study drug accountability checks are being performed.
- Perform source data verification (a comparison of the data in the eCRFs with the subject's medical records at the hospital or practice, and other records relevant to the study) including verification of informed consent of participating subjects. This will require direct access to all original records for each subject (e.g., clinic charts).

- Ensure withdrawal of informed consent to the use of the subject's biological samples is reported and biological samples are identified and disposed of/destroyed accordingly, and the action is documented, and reported to the subject.

The NextCure representative will be available between visits if the investigator(s) or other staff at the center needs information or advice about the study conduct.

10.2.1. Source Data

All source documents should be completed in a neat, legible manner to ensure accurate interpretation of data. Data reported in the eCRF derived from source documents should be consistent with the source documents.

The primary source document for this study will be the subject's medical record. If the investigator(s) maintains separate research records, both the medical record and the research records will be considered the source documents for the purposes of auditing the study.

Data recorded on source documents will be entered into eCRFs. The investigator must promptly review the completed eCRFs for each subject. A study monitor representing the sponsor will review the source documents against the eCRF on a regular basis throughout the study.

The PI at each/the center should comply with all the terms, conditions, and obligations of the Clinical Study Agreement, or equivalent, for this study. In the event of any inconsistency between this Clinical Study Protocol and the Clinical Study Agreement, the terms of Clinical Study Protocol shall prevail with respect to the conduct of the study and the treatment of subjects and in all other respects, not relating to study conduct or treatment of subjects, the terms of the Clinical Study Agreement shall prevail.

Agreements between NextCure and the PI must be in place before any study-related procedures can take place, or subjects are enrolled.

10.2.2. Archiving of Study Documents

The Investigator follows the principles outlined in the Clinical Study Agreement.

10.3. Study Timetable and End of Study

An individual subject will be considered to have completed the study if the subject was followed through the last protocol-specified visit/assessment (including telephone contact), regardless of the number of doses of investigational product that was received.

Subjects will be considered not to have completed the study if consent was withdrawn or the subject was lost to follow-up (see [Section 5.5.1](#)).

The end of the study ("study completion") is defined as the date of the last protocol-specified visit/assessment (including telephone contact) for the last subject in the study.

10.4. Data Management

Data management will be performed by Syneos Health, on behalf of NextCure, according to the study specific Data Management Plan.

A Web Based Data Capture (WBDC) system will be used for data collection and query handling. The investigator will ensure that data are recorded on the eCRFs as specified in the study protocol and in accordance with the instructions provided.

The investigator ensures the accuracy, completeness, and timeliness of the data recorded and of the provision of answers to data queries according to the Clinical Study Agreement. The investigator will sign the completed eCRFs. A copy of the completed eCRFs will be archived at the study site.

10.5. Medical Monitor Coverage

Each subject will be provided with contact information for the PI and the site coordinator(s). In an emergent situation, a subject may present to a medical facility where the treating health care provider is not involved with this clinical trial. The treating healthcare provider may require additional information on the study drug, and the subject should provide contact information for the site coordinator(s) or the PI.

The PI will then be required to update the medical monitor.

11. ETHICAL AND REGULATORY REQUIREMENTS

11.1. Ethical Conduct of the Study

The study will be performed in accordance with ethical principles that have their origin in the Declaration of Helsinki and are consistent with ICH/Good Clinical Practice (GCP), and applicable regulatory requirements.

11.2. Subject Data Protection

The ICF will incorporate (or, in some cases, be accompanied by a separate document incorporating) wording that complies with relevant data protection and privacy legislation.

The anonymity of subjects must be maintained. Subjects will be identified by their initials and an assigned subject number on eCRFs and other documents submitted to the sponsor. Documents that identify the subject beyond initials and subject number will not be submitted to the sponsor (e.g.; the signed ICF) and must be maintained in strict confidence by the investigator, except to the extent necessary to allow auditing by the regulatory authorities, site monitor, or sponsor representatives.

NextCure will not provide individual genotype results to subjects, any insurance company, any employer, their family members, general physician, or any other third party, unless required to do so by law.

Extra precautions are taken to preserve confidentiality and prevent genetic data being linked to the identity of the subject. In exceptional circumstances, however, certain individuals might see both the genetic data and the personal identifiers of a subject. For example, in the case of a medical emergency, a NextCure medical monitor or an investigator might know a subject's identity and also have access to his or her genetic data. Also, Regulatory authorities may require access to the relevant files, though the subject's medical information and the genetic files would remain physically separate.

11.3. Ethics and Regulatory Review

An IRB/IEC should approve the final study protocol, including the final version of the ICF and any other written information and/or materials to be provided to the subjects. The investigator will ensure the distribution of these documents to the applicable IRB/IEC, and to the study site staff.

The opinion of the IRB/IEC should be given in writing. The investigator should submit the written approval to NextCure before enrollment of any subject into the study.

The IRB/IEC should approve all advertising used to recruit subjects for the study.

NextCure should approve any modifications to the ICF that are needed to meet local requirements.

If required by local regulations, the protocol should be re-approved by the IRB/IEC annually.

Before enrollment of any subject into the study, the final study protocol, including the final version of the ICF, is approved by the national regulatory authority or a notification to the national regulatory authority is done, according to local regulations.

NextCure will handle the distribution of any of these documents to the national regulatory authorities.

NextCure will provide Regulatory Authorities, IRB/IEC, and PIs with safety updates/reports according to local requirements, including suspected unexpected serious adverse reactions (SUSARs), where relevant.

Each PI must inform the IRB/IEC of:

- Changes in informed consent
- Revisions of other documents originally submitted for review
- Serious and/or unexpected AEs occurring during the study
- New information that may adversely affect the safety of subjects or the conduct of the study
- Annual update and/or request for re-approval
- Study completion

